#### **13.2.15. Assessment of the acceptability of trial interventions**

At the start of cycle 4 and at the end of study visit (1 month after the last chemotherapy treatment), the patient will be asked to complete a short questionnaire.

#### **13.3. Eligibility Check and Randomisation**

Following all baseline assessments, eligibility must be confirmed per section 10. and 11., prior to randomisation, per section 11.

## **14. Trial Intervention**

### **14.1. Description of the Investigational Medicinal Product**

Enalapril is an Angiotensin Converting Enzyme (ACE) inhibitor which suppresses the renin-angiotensin-aldosterone system resulting in increased plasma renin activity and decreased aldosterone secretion. This trial aims to investigate the prevention of cardiac damage in patients treated for breast cancer using the pharmaceutical actions of enalapril.

This trial will use enalapril at doses from 2.5mg to 10mg twice daily using dose escalation depending upon the response and maximum tolerated doses in this patient group. Any brand of enalapril 2.5mg, 5mg, or 10mg tablets may be used during this trial. Further details relating to the properties of enalapril can be found in the summary of product characteristics (SmPC).

### **14.2. Manufacture of Enalapril**

Product licensed packs of enalapril tablets will be purchased by Nottingham University Hospitals NHS Trust (NUH), pharmacy production unit. As this is an open-label study, there is no blinding of the product required and therefore the product will remain within its original primary packaging as a minimum. The Qualified Person (QP) who will release the final packed products will be a member of the NUH quality team who is authorised to release investigational medicinal products (IMPs) and named on the MIA(IMP) licence.

### **14.3. Packaging and labelling of Enalapril**

NUH Pharmacy Production Units (MIA(IMP) 19162) will supply enalapril in pack sizes of 10 and 28 tablets. For those strengths of enalapril (2.5mg and 5mg) which will be supplied in packs of 10, the product will remain within the original sealed blister strip which will be assembled into plain white cardboard cartons each containing 10 tablets. The pack sizes of 28 tablets (2.5mg, 5mg, 10mg) will remain within the original primary and secondary packaging as supplied by the manufacturer. As a result of the primary packaging being retained intact, the product will maintain the original product shelf life and no further stability studies will be undertaken.

Each pack, 10 tablets or 28 tablets, will be labelled in accordance with EU Guidelines to Good Manufacturing Practice, Medicinal Products for Human and Veterinary Use, Annex 13, Investigational Medicinal Products and the Clinical Trials Directive 2001/20/EC. Each label will state the product name, batch number, expiry date, storage conditions and a space to allow the patient's name to be completed at the point of dispensing. All other details will be compliant with the annex 13 labelling requirements.

### **14.4. Storage, dispensing and return**

The packs of enalapril will be stored in the designated clinical trials pharmacy at participating centres which are secure departments with temperature controls and continuous temperature monitoring. The

storage conditions for the IMP will be at or below 25°C with a warning that the product must not be refrigerated or frozen. A supply of IMP will be made for a patient upon presentation of a trial specific prescription to the clinical trials pharmacy at participating centres. The prescription may be written by a clinician or persons trained and qualified to do so (e.g., prescribing pharmacist or nurse), prescribers must be recorded on the study delegation log. Upon receipt of a trial specific prescription, pharmacy will dispense the corresponding strength of IMP to the patient. At the point of dispensing, pharmacy will complete the dispensing labels and accountability logs to allow the products to be traced.

Any unused IMP will be returned to the clinical trials pharmacy at the end of the treatment period to allow for final accountability and destruction of the product in accordance with local policy.

#### **14.5. Known side effects**

Very common side effects related to treatment with enalapril include: cough, dizziness, nausea, asthenia, blurred vision, and hyperkalaemia. Common and severe side effects include angioedema and renal impairment. More detailed information relating to the side effects of enalapril can be found in the SmPC for the product. See Appendix 1.

#### **14.6. Administration of Enalapril**

Following randomisation, patients randomised to receive Enalapril may begin taking the drug. The patient needs to have received at least 5 days of enalapril prior to their first dose of epirubicin-based adjuvant chemotherapy.

The trial aims to have all patients in the enalapril arm on a dose of 10mg BD, however clinical judgement alongside clinical assessments will be used to determine the maximum tolerated dose (MTD) for the patient, up to a maximum of 10mg BD. Dose titration and evaluation visits are described below. Chemotherapy will not be delayed by taking part in the trial.

##### **14.6.1. Dosing visit day 1**

Patients will be dispensed 2.5mg enalapril BD as their starting dose to begin taking that day.

##### **14.6.2. Dose evaluation visit 1**

Two to five days after the start of enalapril, the patient should return for a dose evaluation visit. Blood pressure and U&Es should be measured and the patient should be assessed for side effects.

If the patient has systolic BP  $\geq$ 100 mmHg, normal serum potassium (potassium  $<$ 5.5 mmol/L), and stable renal function (serum creatinine  $<$ 30  $\mu$ mol/L increase from baseline over 48-96 hours) then the enalapril dose should be up-titrated to 5mg BD.

If the patient is, in the clinical opinion of the investigator, unlikely to tolerate a higher dose at this point then the dose should remain the same. At the discretion of the investigator, a further assessment at

dose evaluation visit 2 could be made to consider up-titration of enalapril to 5mg BD using the same criteria as above.

If the patient has a  $\geq 30$   $\mu\text{mol/L}$  increase in serum creatinine levels since the last assessment compared to baseline, new hyperkalaemia (potassium  $\geq 5.5\text{mmol/L}$ ), or symptomatic hypotension (SBP  $< 100\text{mmHg}$ ) then enalapril should be permanently discontinued and the patient withdrawn from the study. The patient should be seen again within 7 days to ensure the reasons for withdrawal have resolved to the satisfaction of the investigator.

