#### **13.2.9. Urea and Electrolytes (U&Es)**

U&Es (Urea, Na+, K+ and Creatinine) will be assessed at baseline, at each dose evaluation visit (enalapril arm only), and within 72 hours prior to the intended day 1 at the start of chemotherapy at cycle 2, 3, 4, 5, 6 and at one month after the last epirubicin dose.

Samples will be collected, processed and analysed in accordance with local hospital practice, with the results recorded in the eCRF. These blood samples are often taken and tested routinely, if this is the case, and they fit within the windows for the trial, repeat tests specifically for the trial are not needed.

If serum creatinine levels increase by 30 µmol/L over 48-96 hours, or increases to >1.5 times the baseline value, the clinical judgement of the Principal Investigator should be sought, and/or the Chief Investigator, to confirm the action to be taken, which may require a temporary or permanent halt to enalapril (for those in the enalapril group).

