#### **14.6.3. Dose evaluation visit 2**

Two to five days after dose evaluation visit 1, if the dose of enalapril was increased, the patient should return for a second dose evaluation visit. Blood pressure and U&Es should be measured and the patient should be assessed for side effects.

If the patient has systolic BP  $\geq 100$  mmHg, normal serum potassium (potassium  $< 5.5$  mmol/L), and stable renal function (serum creatinine  $< 30$   $\mu\text{mol/L}$  increase since last assessment, or a  $< 1.5$  times increase from baseline) then the enalapril dose should be up-titrated to 10mg BD.

If the patient is, in the clinical opinion of the investigator, unlikely to tolerate a higher dose, then the dose should remain the same.

If the patient has a  $\geq 30$   $\mu\text{mol/L}$  increase in serum creatinine levels since the last assessment, or a  $\geq 1.5$  times increase from baseline, potassium  $\geq 5.5\text{mmol/L}$ , or symptomatic hypotension (SBP  $< 100\text{mmHg}$ ) then reduce back to previously tolerated dose and recheck blood pressure, and U&Es two to five days later.

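### The visit 1 up-titration rule has no 1.5-times-baseline creatinine limit, so it raises the dose by default on results that section 13.2.9 refers for a possible halt (baseline below 60 µmol/L only)

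*Combined protocol and SAP*

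**What the plan says.** Section 14.6.2 (dose evaluation visit 1) sets three conditions for moving from 2.5 mg to 5 mg twice daily: adequate systolic pressure, potassium below 5.5 mmol/L, and a creatinine rise under 30 µmol/L. The creatinine condition and the instruction that follows end: "increase from baseline over 48-96 hours) then the enalapril dose should be up-titrated to 5mg BD". The stopping rule at the same visit also uses only the 30 µmol/L limit.

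Section 13.2.9 requires U&Es "at each dose evaluation visit (enalapril arm only"), so it applies at visit 1. It has two creatinine triggers. One is a 30 µmol/L rise over 48-96 hours. The other applies when creatinine "increases to >1.5 times the baseline value, the clinical judgement of the Principal Investigator should be sought", and/or that of the Chief Investigator, about an action "which may require a temporary or permanent halt to enalapril (for those in the enalapril group").

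Discretion is preserved. Section 14.6 says "clinical judgement alongside clinical assessments will be used to determine the maximum tolerated dose". Section 14.6.2 adds that for a patient judged "unlikely to tolerate a higher dose at this point then the dose should remain the same". In that case a further assessment at "dose evaluation visit 2 could be made to consider up-titration of enalapril to 5mg BD using the same criteria as above".

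Sections 14.6.3 and 14.6.4 (visits 2 and 3) do carry a 1.5-times-baseline term. In the visit 2 up-titration sentence it is joined to the 30 µmol/L limit by *or*: "increase since last assessment, or a" less than 1.5-fold increase from baseline.

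**The concern.** Visit 1 is the first scheduled renal check on enalapril, and it is the only dose evaluation visit whose rules omit the ratio to baseline. A patient with a low baseline can therefore have creatinine more than 50% above baseline and still be classed as stable, with a dose increase as the written default. For the same result, another section asks for a decision on whether to stop the drug.

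The person applying section 14.6.2 need not be the one named in section 13.2.9, because section 6 lets a delegated sub-investigator make trial medical decisions. Section 14.6.2 has no cross-reference to the referral. If the dose is held at visit 1, the same incomplete criteria are reused at visit 2 for the step to 5 mg, so the gap can recur.

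What is at stake is a dosing-safety instruction. The endpoints, the analysis and the sample size are not affected.

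**Working it through.** The plan gives no figure to reproduce here; the check is threshold algebra. Let B be baseline creatinine, C the visit 1 value, and C1 and C2 the visit 1 and visit 2 values, all in µmol/L.

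**Inputs**
- Visit 1 up-titration (14.6.2): C − B < 30.
- Referral (13.2.9): C > 1.5B.
- Visit 2 up-titration (14.6.3): C2 − C1 < 30 *or* C2 < 1.5B.
- Visit 2 reduction (14.6.3): C2 − C1 ≥ 30 *or* C2 ≥ 1.5B.

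**Step 1: visit 1 overlap.** Both visit 1 rules are met when 1.5B < C < B + 30. This interval is non-empty only if 1.5B < B + 30, that is B < 60. Its width is 30 − 0.5B. In whole numbers:

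| B | 1.5B | Values meeting both rules | Count | Highest ratio |
|---|---|---|---|---|
| 40 | 60 | 61-69 | 9 | 69/40 = 1.73 |
| 45 | 67.5 | 68-74 | 7 | 74/45 = 1.64 |
| 50 | 75 | 76-79 | 4 | 79/50 = 1.58 |
| 55 | 82.5 | 83-84 | 2 | 84/55 = 1.53 |
| 56 | 84 | 85 | 1 | 85/56 = 1.52 |
| 57 | 85.5 | 86 | 1 | 86/57 = 1.51 |
| 58 or above | 87 or above | none | 0 | – |

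Example: B = 50, C = 77. The rise is 27, under 30, so section 14.6.2 up-titrates. The ratio is 77/50 = 1.54, above 1.5, so section 13.2.9 refers. None of the tabulated values meets the visit 1 stopping rule, which needs a rise of 30 or more.

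**Step 2: effect of adding C ≤ 1.5B at visit 1.** The overlap with C > 1.5B is then empty at every B. For B ≥ 60 nothing changes, because C < B + 30 already implies C < 1.5B.

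**Step 3: the visit 2 sentence.** Because its limits are joined by *or*, one result can meet both the up-titration and the reduction rule, in two ways.
- *Rise under 30, ratio at least 1.5.* Example: 80, 100, 121. The rise since visit 1 is 21 and 121/80 = 1.51. If both rises are under 30, the total rise is at most 29 + 29 = 58 and must reach 0.5B, so B ≤ 116 (116, 145, 174 gives exactly 1.50; 117, 146, 175 gives 1.496).
- *Rise of 30 or more, ratio below 1.5.* Example: 120, 120, 155. The rise is 35 and 155/120 = 1.29. If the visit 1 value equals baseline, this needs 30 < 0.5B, so it can occur at any baseline above 60, with no upper limit.

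With *and* in place of *or*, up-titration requires C2 − C1 < 30 and C2 < 1.5B. That is the exact complement of the reduction rule, so both overlaps disappear.

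**The case against.** The best defence is that the two sections do not order opposite actions. Section 13.2.9 applies at visit 1 whatever section 14.6.2 says. It asks for judgement, with a halt only as a possibility, and the investigator may hold the dose. A site that reads both sections will seek advice. Anyone who is up-titrated is rechecked two to five days later under a rule that reduces the dose at 1.5 times baseline. The trigger needs a low baseline and a rise of more than half within days of starting 2.5 mg twice daily, and the number of such patients may be zero. All of this stands, and it keeps the consequence small. It does not make the default right: the discretionary hold carries no creatinine trigger, and a reader of section 14.6.2 alone is told that this patient is stable.

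A second objection is that, read strictly, the visit 1 rise must be measured over 48-96 hours. The schedule in section 13.1 has no Day 1 U&E and allows baseline up to 6 weeks before randomisation, so the window often could not be assessed and stability would not be shown. That is a fair point about the wording, but the rule would then be unworkable for many patients. The natural working reading compares visit 1 with the baseline sample.

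Third, the fix leaves some matters open. A value of exactly 1.5 times baseline (58 to 87) would still be up-titrated at visit 1, although visit 2 acts at that ratio; it does not conflict with section 13.2.9, which acts only above 1.5. The sections also differ on a rise of 30 µmol/L or more, where 13.2.9 leaves the action to judgement and 14.6.2 requires permanent discontinuation and withdrawal. That is a separate point, which this fix does not address.

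**Conclusion.** The concern holds, as a minor inconsistency between sections with a wrong default as written. It affects patients with baseline creatinine below 60 µmol/L (57 or below in whole numbers) whose visit 1 value falls in a band 30 − 0.5B wide. How many that is cannot be estimated from the documents.

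Two readings are assumed. First, the visit 1 rise is measured against the baseline sample. Second, a 1.5-times increase in sections 14.6.3 and 14.6.4 means reaching 1.5 times baseline, as in section 13.2.9. The visit 1 conflict does not depend on the second reading. The visit 2 ceiling for rises each under 30 does: if the phrase meant a rise of 1.5B, the ceiling would fall from 116 to 38 (1.5 × 38 = 57, within the maximum total rise of 58; 1.5 × 39 = 58.5, beyond it).

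**What to change.** - **Section 14.6.2:** define stable renal function for up-titration as a rise below 30 µmol/L from baseline *and* creatinine not above 1.5 times baseline. State that a patient above 1.5 times baseline with a rise under 30 is not up-titrated and is referred under section 13.2.9. The same definition then governs visit 2 wherever 14.6.2 reuses its criteria.
- **Section 14.6.3:** in the up-titration sentence, change *or* to *and* so that both creatinine limits must be met.
- **Section 13.2.9:** leave unchanged, so that the referral continues to apply at every dose evaluation visit.

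The cost is one added criterion, one changed word and a notice to sites, with no extra visits, samples or patients.

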### 12.2. Withdrawal of participants

Patients may withdraw from the trial at any time if they wish to, without giving reason and without any adverse consequences for their ongoing clinical management. Patients in the intervention arm will need to stop taking enalapril maleate on the day they withdraw, and return all unused drug to the clinical research team.

All patients will be made aware of their right to withdraw from the study, and this information will be included in the patient information sheet.

Patients should be withdrawn from the trial by the clinical team if:

- the patient suffers unacceptable side effects caused by enalapril maleate;
- the patient becomes ineligible between randomisation and commencement of chemotherapy;
- the patient becomes pregnant or there is evidence that a patient fails to use adequate birth control;
- the patient has disease recurrence.

Data and blood samples for troponin assessment collected up to the point of withdrawal will be kept and used in the analysis of the trial.

Patients will be asked upon withdrawal:

- whether further data can continue to be collected from their medical records;
- whether samples collected for future research may still be analysed;
- whether they may be approached in future research connected to the trial.

This information will be captured on a withdrawal form, to be stored in the ISF and a copy of which sent to NCTU (by email), this will also be captured in the eCRF.

Data from patients who withdraw will remain in the overall analysis; however, dependent on the stage of withdrawal, then further patients may be recruited to ensure that the sample size is reached.

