#### **Blinded end-point blood samples**

After randomisation, up to 5mL of blood will be collected in an SST, processed immediately after collection, stored and transported as described in the PROACT laboratory manual. These samples will be taken within 72 hours prior to the intended start of chemotherapy at cycle 2, 3, 4, 5, 6 and at one month after the last epirubicin dose. These samples will be taken to coincide with standard pre-chemotherapy bloods, where possible. If the local processing laboratory finds that the samples collected are haemolysed, a repeat sample will be requested immediately. If chemotherapy is delayed by the clinical team, further study blood samples for troponin will not be required.

Troponin T will be batch-tested in a blinded manner for this trial and data will be entered into the eCRF by the central laboratory teams.

Troponin I will be batch-tested in a blinded manner at the end of the trial and the result entered into the eCRF by central teams.

Any remaining serum after analysis will be discarded.

The research team will not be made aware of the results of the troponin testing until the end of the trial. The results will not be available for the patients or treating clinicians.

A full chain of custody will be maintained for each sample throughout its lifecycle. The principal investigator at each study site will keep full traceability of collected samples while in storage at site until shipment or disposal and keep records of shipping for each sample. The receiver will acknowledge receipt of each sample and keep full traceability of the samples whilst in storage and during use until used or disposed of.

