#### **14.6.5. Continuation of treatment with enalapril**

Once the patient is on their maximum tolerated dose of enalapril they should receive this dose daily throughout the trial (including on chemotherapy treatment days). There may be instances where a patient has side effects to their cancer, chemotherapy or to enalapril that require a temporary halt to

taking enalapril. Temporary halts of up to 7 days (14 doses) will be allowed within the trial. These should be noted and explained. Where this due to an intolerance of enalapril, only one temporary halt will be allowed. Where the intolerance has manifested as angioedema, then treatment with enalapril should be withdrawn.

Re-introduction of enalapril may be at the discretion of the local clinician. It is recommended that where temporary halts are due to chemotherapy-related toxicities, then reintroduction at the established MTD is acceptable. Where temporary halts have been due to renal instability then reintroduction at a dose lower than the MTD is recommended.

Dose reductions of enalapril in routine use would not be expected; in this study they will be allowed and at the discretion of the investigator.

Any re-introduction or dose adjustment of enalapril must be followed 2-5 days after the re-introduction/adjustment to assess blood pressure and U&Es.

At each attendance prior to the start of a new cycle of chemotherapy, patients will be asked about how much enalapril they have left and a new prescription dispensed if required.

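### Two withdrawal rules that only the enalapril arm can trigger take patients out of the study, so primary-outcome data are likely to be lost in that arm alone

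*Combined protocol and SAP*

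**What the plan says.** Section 14.6.2 (Dose evaluation visit 1) names two separate actions for a rise in creatinine, new hyperkalaemia or symptomatic hypotension: "then enalapril should be permanently discontinued and the patient withdrawn from the study". Section 12.2 tells the clinical team to withdraw a patient from the trial if "the patient suffers unacceptable side effects caused by enalapril maleate", and also if "the patient becomes ineligible between randomisation and commencement of chemotherapy".

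After withdrawal, section 12.2 keeps data and troponin samples only up to that point. It then asks the patient three things: "whether further data can continue to be collected from their medical records", whether stored research samples may still be analysed, and whether the patient may be approached about future research. Section 19.8 adds that primary-endpoint data can be collected from a withdrawn patient who agrees.

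On endpoint sampling, section 13.2.8 says "These samples will be taken within 72 hours prior to the intended start of chemotherapy at cycle 2" and at later cycles, with a last sample one month after the final epirubicin dose. Of the troponin results it says: "The results will not be available for the patients or treating clinicians".

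The Statistical Analysis section (the second heading numbered 17.1) promises an intention-to-treat primary analysis, regardless of treatment actually taken, with full effort to keep all patients in. It gives no rule for a patient without post-baseline troponin and defers detail to a separate SAP that is not among the documents supplied.

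**The concern.** The rules join two decisions that should be separate: stopping enalapril and leaving follow-up. Only the enalapril arm takes the drug and attends dose evaluation visits, so any resulting loss of primary-outcome data falls on that arm and is caused by treatment. If those patients are then dropped, patients who tolerated enalapril are compared with all controls. That is unbiased only if those withdrawn have the same troponin risk as those retained, and the trial could not check this without their samples.

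The ineligibility rule in section 12.2 applies to both arms but is not checked equally. The trial schedules U&Es between randomisation and cycle 1 only "at each dose evaluation visit (enalapril arm only").

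The protocol is also inconsistent. For angioedema, section 14.6.5 withdraws the drug and does not mention the study: "Where the intolerance has manifested as angioedema, then treatment with enalapril should be withdrawn". Section 13.2.9 speaks of a temporary or permanent halt to enalapril after a creatinine rise, where section 14.6.2 requires permanent discontinuation and study withdrawal. These passages need to be reconciled; no view is taken here on which clinical rule is right.

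**Working it through.** **The plan's own figure.** The inputs from section 17.1 are 47% v 20%, a two-sided Fisher's exact test, alpha 5% and 90% power. The continuity-corrected formula for two proportions gives 70 per arm, or 140, as stated. Exact enumeration gives 90.8% power at 70 per arm and 95.4% at 85 per arm. The step to 170 implies an attrition allowance of 1 − 140/170 = 17.6%, with no split by arm.

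**Timing.** Enalapril starts at least 5 days before cycle 1 (section 14.6), and visit 1 is 2 to 5 days after that start. Visit 1 is therefore on or before cycle 1 day 1. Cycles are 21 days apart, and the first endpoint sample is at most 3 days before cycle 2, so it comes at least 21 − 3 = 18 days later. A patient withdrawn at visit 1 has only the baseline troponin T, which is below 14 ng/L by eligibility.

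**Can the outcome be recovered?** Medical records cannot supply it, because results are withheld from treating clinicians. The route in section 19.8 needs new trial blood, which the section 12.2 questions do not ask about. Loss is therefore likely but not certain.

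**Size.** The documents give neither the share withdrawn nor its risk, so both are assumed. Let w be the share of 85 enalapril patients withdrawn unsampled, from 5% to 20%, with all 85 controls sampled. Probabilities are exact, summed over binomial outcomes, rejecting at p ≤ 0.05. The chance of a false result favouring enalapril is 1.9% with full data.

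- (a) Dropped, no drug effect, everyone at 47%.
- (b) Dropped, retained at 20%, withdrawn at 47%. The true all-randomised rate is 0.20(1 − w) + 0.47w, but 20% is observed, so the overstatement is 0.27w.
- (c) Dropped, no drug effect (47% overall), withdrawn patients 13 points above (60%) or below (34%). The retained rate is (0.47 − w·r)/(1 − w), where r is the withdrawn patients' risk.
- (d) No drug effect, unsampled patients scored as absence, so the rate is 0.47(1 − w) with n = 85. No passage states this scoring.

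| w | n sampled | (a) false result | (b) true rate; overstatement | (c) bias either way | (c) false result, r = 60% / 34% | (d) false result |
|---|---|---|---|---|---|---|
| 5% | 81 | 2.2% | 21.35%; 1.35 points | 0.7 points | 2.8% / 1.8% | 3.8% |
| 10% | 77 | 2.0% | 22.7%; 2.7 points | 1.4 points | 3.1% / 1.3% | 7.1% |
| 15% | 72 | 1.9% | 24.05%; 4.05 points | 2.3 points | 3.6% / 0.9% | 12.2% |
| 20% | 68 | 1.9% | 25.4%; 5.4 points | 3.3 points | 4.9% / 0.7% | 19.6% |

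**Tipping point.** Take 40/85 control events. With 12 enalapril patients missing (12/85 = 14%), 15/73 gives p = 0.0007. Counting all 12 as positive gives 27/85 and p = 0.059. With 10 missing, 15/75 gives p = 0.0004 and 25/85 gives p = 0.027.

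**The case against.** The strongest reply is that the remedy already exists. Section 19.8 allows primary-endpoint data from a withdrawn patient who agrees and commits to including them, and the Statistical Analysis section promises retention efforts. The list of questions in section 12.2 is not called exhaustive, and the withdrawal form is not among the documents. That stands as a reason to call the loss likely, not certain. It does not remove the problem, because staff following sections 14.6.2 and 12.2 are told to withdraw the patient and are not pointed to section 19.8.

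The scenarios may also be too large. Visit 1 follows only a few days on the starting dose, in patients already screened for low blood pressure and high potassium. Side-effect withdrawals under section 12.2 can come later, when some samples exist and a positive already settles the outcome. This is fair. With 2% to 3% unsampled, the overstatement in case (b) is only 0.27 × 2 to 0.27 × 3, or 0.5 to 0.8 points. The false-result chance in case (c) at 60% risk is then 2.4% to 2.6%. The 13-point gap in case (c) has no source in the documents.

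Two supporting points carry less weight than they first appear to. Visits 2 and 3 reduce the dose for similar findings, but at visit 1 the patient is on the starting dose and has no previously tolerated dose to return to, so that contrast is partly about dosing. And section 13.2.7 schedules blood pressure before cycle 1 in both arms, so the unequal checking of eligibility rests on the U&Es alone. Finally, the unseen SAP may already state a missing-data method, but it cannot recover samples that were never taken.

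**Conclusion.** The concern holds. It is certain from the text that the two rules remove patients from the study, that only the enalapril arm can trigger them, and that visit 1 precedes every endpoint sample. The resulting one-sided loss is likely and conflicts with the stated intention-to-treat analysis.

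Its size and direction cannot be known from the documents. Under the assumed 5% to 20% loss, the effect on the estimate runs from none (equal risk) to an overstatement of 5.4 points (withdrawn patients at control risk). It reverses if withdrawn patients are at lower risk than those retained. The larger false-result chances in case (d) apply only if a missing outcome were scored as absence. Spare numbers in the 170, or the replacement recruitment allowed by section 12.2, restore sample size but not comparability. This should be fixed; confidence in its practical importance is medium.

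**What to change.** Leave the enalapril stopping criteria as they are, and change what follows from them.

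1. Reconcile sections 14.6.2, 12.2, 14.6.5, 19.8 and the Statistical Analysis section so that a patient who stops enalapril stays, with continuing consent, in follow-up for the planned troponin samples, final echocardiogram and adverse event visits.
2. Add continued trial blood sampling and the final echocardiogram to the withdrawal questions in section 12.2.
3. State whether a patient in either arm who becomes ineligible after randomisation stays in endpoint follow-up.
4. In the SAP, unless already there, state the missing-outcome method and do not score a patient with missing samples and no positive as absence. Add sensitivity analyses: missing-as-positive in the enalapril arm, and imputation for off-drug patients that does not borrow only from those who tolerated enalapril (for example, control-based).

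The cost is protocol wording, the withdrawal form and SAP text; the samples already coincide with routine pre-chemotherapy bloods where possible. The downside is power. If 10%, 15% or 20% of the enalapril arm reverts to 47% risk and everyone is followed, exact power at 85 per arm falls from 95.4% to 89.4%, 85.0% or 79.7%, below the 90% target. That is the power for the effect the protocol says it will estimate.

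Analysis alone is a poor substitute. With 15% unsampled and 20% risk in the rest, missing-as-positive gives 0.20 × 0.85 + 0.15 = 32% and only a 46% chance of significance.
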